Based on the results of the previously conducted BE trial, a within-subject Coefficient of Variation (CV) for $AUC_{0\rightarrow t}$ and C_{max} has been calculated. In previous studies, GIR formulation has shown relatively low intra-individual CV. With 20 evaluable subjects in the fasting and 12 subjects in the fed group will provide at least 90% power and 99.7% power to show BE in the fasting group and in the fed group respectively, resulting in nearly 90% power to get both. For a compensation of possible drop-outs, a total of 26 subjects will be included in the fasting group and 18 subjects in the fed group, corresponding to a drop-out rate of around 25%. In total, 44 subjects should be included in the trial.

Primary Endpoint analysis

The analysis of Primary Endpoints will be based on PK Population The primary variable, C_{max} and $AUC_{0\rightarrow t}$ in fasting and fed group will be log-transformed and mixed effect model will be applied. The model will include effects for sequence, treatment and period. Subject within sequence will be included as random effect. Bioequivalence will be assessed separately, in the fed and in the fasted group, and the trial will be successful only, if BE has been established in both groups.

Based on the residual (within-subject) variation, 90% CIs for the ratio of geometric means will be calculated. The BE can be established if the 90% CI on the ratios between test and reference of the geometric means fall within 80.00% to 125.00%.

Secondary Endpoint analysis

For t_{max} , the Hodges-Lehmann estimates for the pairwise treatment differences and the corresponding 90% CIs according to the Tukey method will be calculated. The mixed model as described above will also be applied to $AUC_{0\to\infty}$. A 90% CI will be calculated for the ratios of geometric means of the test IMP and reference IMP. Summaries using descriptive analyses will be applied for the remaining PK parameters.

For safety endpoints, all data recorded during the trial will be presented in individual data listings performed on the Safety Population. All safety variables will be analyzed using descriptive statistics. The continuous variables will be summarized descriptively per treatment, period, time point, and overall by N, arithmetic mean, median, standard deviation (SD), standard error of the mean (SEM), and minimum and maximum values. Categorical variables

GIR China Bioequivalence Study

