10.2 Definition of Analysis Sets and Subgroups

Screening Population

The Screening population includes all subjects who have signed the main informed consent (i.e., screening failures plus subjects enrolled).

Safety Population

The Safety Population includes all subjects who received at least 1 dose of IMP. In general, clinical data will be analyzed for the Safety Population.

Pharmacokinetic Population

The PK Analysis Set includes all subjects who completed the trial with adequate trial medication compliance, without any relevant protocol violations or events with respect to factors likely to affect the comparability of PK results, and with sufficient evaluable data to determine primary endpoints ($AUC_{0 \rightarrow t}$ and C_{max}) for both treatments. If subjects receive concomitant medication that potentially affects PK for the treatment of an AE, their inclusion in the PK Analysis Set will be decided on a case-by-case basis. Emesis occurring within two times of the median t_{max} for a given treatment will be considered a relevant event likely to affect the comparability of PK results. Similarly, a predose concentration for a given treatment period which exceeds 5% of C_{max} will be considered a relevant event affecting PK results. All PK analyses will be based on the PK Analysis Set. Data for subjects excluded from the PK Analysis set will be included in listings.

11 General Specifications for Statistical Analyses

Output Presentations:

The shells provided with this SAP describe presentations for this study and therefore the format and content of the summary tables, listings and figures to be provided by IQVIA Biostatistics. Unless otherwise indicated all analyses will be presented separately for the two treatments (Treatment A and Treatment B) and for two treatment sequences (Sequence A-B and Sequence B-A) under different food condition (fed and fasted).

Listings

All listings will be reported separately by food condition and sorted by treatment or treatment sequence (A-B or B-A), and/or scheduled time point, as appropriate. Data which are only collected before administration of trial drug and/or at end of study will be sorted by subject and scheduled time point (if appropriate).

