Descriptive statistics of PK concentration data will be calculated using values with the same precision as the source data, and rounded for reporting purposes only. The following conventions will be applied when reporting descriptive statistics of PK concentration data:

| | |
|-------------------------|----------------------|
| Mean, Min, Median, Max: | 3 significant digits |
| SD: | 4 significant digits |
| CV%: | 1 decimal place |

Descriptive statistics of plasma concentrations below the LLOQ will be taken as zero.

Presentation of PK Parameter Data

Pharmacokinetic parameter data will be descriptively summarized using: N, Mean, SD, CV%, Min, Median, Max, geometric mean (GeoMean), the geometric coefficient of variation (GeoCV%), and the 95% CI for the GeoMean (LCI 95% GM, UCI 95% GM).

Descriptive statistics of PK parameter data will be calculated using full precision values, and rounded for reporting purposes only.

The following conventions will be applied when reporting descriptive statistics of PK parameter data:

| | |
|--|----------------------|
| Mean, Min, Median, Max, GeoMean, 95% CI: | 3 significant digits |
|--|----------------------|

| | |
|----------------|----------------------|
| GeoMean ratio: | 2 decimal places |
| SD: | 4 significant digits |
| CV%, GeoCV%: | 1 decimal place |

Presentation of continuous and qualitative variables

Continuous variables will be summarized using the following descriptive statistics unless otherwise specified, i.e.,

- Number of subjects (N), number of subjects with non-missing values
- Mean, SD
- Median
- Minimum and maximum

Qualitative variables will be summarized by counts and percentages.

Unless otherwise stated, the calculation of proportions will be based on the number of subjects of the analysis set of interest. Therefore, counts of missing observations will be included in the denominator and presented as a separate category.

In case the analysis refers only to certain visits, percentages will be based on the number of subjects still present in the trial at that visit, unless otherwise specified.

Software:

Pharmacokinetic parameters will be derived using noncompartmental methods with the validated computer program Phoenix[®] WinNonlin[®] 6.4 or higher (PPD [REDACTED]). Pharmacokinetic figures will be developed using SigmaPlot[®] 12.5 or higher (PPD [REDACTED]), Phoenix[®] WinNonlin[®] 6.4 or higher, or SAS[®] Windows Version 9.4 or higher (PPD [REDACTED]).

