Any adverse event (AE) with incomplete start/time and or end dates will be handled as described below for the classification as treatment-emergent, assignment to treatment periods, and calculation of duration.

- AE with unknown start time but known start date, will be imputed with a time of 00:00 hours, unless the start date corresponds to any given dosing date, in which case time of dosing will be used instead. However, if this results in a start time after end time of the AE, then the start time will be imputed to 00:00 hours instead.
- Any AE with completely unknown start date will be imputed with date and time of the first IMP administration, unless the end date (imputed if needed) is known and prior to first IMP administration. In the latter case, the start date will be missing.
- AE with partially missing start date but in the same year (when day and month are missing) or in the same month and year (if the day is missing) as first IMP administration then the start date will be replaced by the minimum between first IMP administration and AE resolution date. In all other cases the missing onset day or onset month will be replaced by 01.
- Adverse event with completely unknown end date will be imputed with the date of study completion (or in case of withdrawal, date of discontinuation).

Partially known end dates will be treated as follows:

- If only the day is missing, the last day of the month will be imputed or the date of study completion/discontinuation if earlier.
- If day and month are both missing, then the end date of 31 December will be imputed or the date of study completion/discontinuation if earlier.

Assignment to the different treatment periods will be performed after the imputations have been performed. An AE will be assigned to a specific treatment period if it occurs on or after the IMP administration scheduled for that period and before the IMP administration in the next period (or study completion for the last period).

Trial day:

Trial day will be calculated from the reference start date, and will be used to show start/end day of assessments and events. Reference start date is defined as the day of the first IMP administration in period 1. Trial Day 1 is the day of first IMP administration in period 1. The day before is defined as Trial Day -1 (no Trial Day 0 is defined). Trial day will be calculated accordingly:

- If the date of the event is on or after the reference start date then:

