16.3.5 Analysis of Molecular Marker

Not applicable.

17 Safety Evaluation

Population: Safety Population

The subsections in this section include specifications for summarizing safety endpoints that are common across clinical trials such as adverse events, laboratory tests, ECG recordings and vital signs. Safety analyses will be done on the Safety Population. All safety data will be listed in individual subject listings by group, treatment sequence and subject.

All safety variables will be analyzed using descriptive statistics. For the evaluation of safety parameters, the continuous variables will be summarized descriptively by N, mean, median, SD, Q1-Q3, and minimum and maximum values. Categorical variables will be presented in frequency tables with the counts of observations and corresponding percentages.

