17.1.1 All Adverse Events

A summary table describing all the TEAEs occurring during the trial will be produced overall and by group as well as by treatment for each group using frequency of events and number and percentage of subjects experiencing these events overall and by SOC and PT.

Group/SOC terms will be sorted by decreasing total frequency. Preferred terms (PT) within each group/SOC term will likewise be sorted by decreasing total frequency.

In addition, all TEAEs will be tabulated by severity and relationship to IMP in the same manner.

Multiple occurrences of the same TEAE in one subject during the same treatment in the trial will be counted as multiple events in the frequency counts for adverse events. If a subject experiences more than one occurrence of the same AE during the same treatment in the trial, the subject will only be counted once for that treatment using the worst severity and the strongest relationship.

In case a subject had events with missing and non-missing severities, the maximum of the non-missing severities will be displayed. In case all the TEAEs of a subject are all with missing severities then Moderate will be used unless there is any evidence that it should be Severe.

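### By the SAP's default rule, by-treatment adverse event percentages keep subjects in the denominator of a product they never received, which understates that product's incidence

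*SAP*

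**What the plan says.** SAP 11, under the presentation of continuous and qualitative variables, gives the default: "Unless otherwise stated, the calculation of proportions will be based on the number of subjects of the analysis set of interest". It adds that "counts of missing observations will be included in the denominator and presented as a separate category". It makes one allowance for attrition, which is confined to visit-specific summaries: "percentages will be based on the number of subjects still present in the trial at that visit, unless otherwise specified".

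SAP 10.2 defines the set: "The Safety Population includes all subjects who received at least 1 dose of IMP". The definition covers either product and is not made per product. SAP 17 states that "Safety analyses will be done on the Safety Population".

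SAP 17.1.1 asks for the table of treatment-emergent events overall, by group, and "by treatment for each group using frequency of events and number and percentage of subjects experiencing these events overall and by SOC and PT". It gives no denominator. SAP 17.1.2 (events leading to discontinuation) and Protocol 8.5.4 give none either.

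For the numerator, SAP 11 says: "An AE will be assigned to a specific treatment period if it occurs on or after the IMP administration scheduled for that period". That window closes at the following period's dose, or at study completion for the last period.

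**The concern.** In a crossover each subject is meant to appear in both treatment columns, but a subject who leaves between doses has been exposed to only one product. Under the period-assignment rule none of that subject's events can fall to the second product. Under the default denominator the subject is still counted there, and so is treated as exposed and event-free. The visit-based exception does not help, because a by-treatment table pools Period 1 of one sequence with Period 2 of the other and is not an analysis of certain visits.

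The error need not fall equally on the two products. Protocol 5.5.2 lists adverse events, early emesis and use of prohibited medication among the grounds for withdrawal. If one product led to more Period 1 withdrawals, the other product would collect the unexposed subjects and its rate would be diluted. At stake is the accuracy of the main by-product safety table, which serves the secondary objective of examining safety and tolerability after each product.

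**Working it through.** **Inputs**
- Group sizes, Protocol Synopsis (Statistical methods): "a total of 26 subjects will be included in the fasting group and 18 subjects in the fed group".
- Sequence allocation, SAP 7.2: 1:1, so 13/13 fasting and 9/9 fed.
- Minimum evaluable subjects, Protocol Synopsis and 5.5.1: 20 fasting and 12 fed. Stated drop-out allowance: around 25%.
- Replacement, SAP 7.2: only if a group falls below 20 or 12.

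**The plan's own figures.** The documents print no adverse event percentage. The nearest stated figure is planned enrolment, which indicates how many losses were allowed for. Inflating by 1/(1 − 0.25):
- Fasting: 20/0.75 = 26.7, rounded up to 27 (stated 26; implied drop-out 6/26 = 23.1%).
- Fed: 12/0.75 = 16 (stated 18; implied drop-out 6/18 = 33.3%).
- Total: 32/0.75 = 42.7, rounded up to 43 (stated 44; implied drop-out 12/44 = 27.3%).

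These agree to within two subjects. The gap between enrolment and the floor is six in each group.

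**Formula.** Let N be the food group's Safety Population, d the number in it never dosed with a given product, and x the number with an event on that product.
- Incidence among those exposed: x/(N − d).
- Printed incidence: x/N = incidence among those exposed × (N − d)/N.
- Relative understatement: d/N.

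**Results** (all enrolled subjects dosed in Period 1, no replacements)

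| d | Fasting, N = 26 | Fed, N = 18 |
|---|---|---|
| 0 | 0 | 0 |
| 1 | 1/26 = 3.8% | 1/18 = 5.6% |
| 2 | 2/26 = 7.7% | 2/18 = 11.1% |
| 3 | 3/26 = 11.5% | 3/18 = 16.7% |
| 4 | 4/26 = 15.4% | 4/18 = 22.2% |
| 6 | 6/26 = 23.1% | 6/18 = 33.3% |

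The d = 6 row needs all six losses to occur between the two doses and in one sequence (6 of 13 fasting, 6 of 9 fed). If six losses split evenly between sequences, each product is missed by three, and the d = 3 row applies to both columns.

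**Illustration, assuming a true incidence of 20% on both products** (the 20% is not in the documents)
- One subject missing a product: 20% × 25/26 = 19.2% fasting; 20% × 17/18 = 18.9% fed.
- Six, split evenly: 20% × 23/26 = 17.7% fasting; 20% × 15/18 = 16.7% fed.
- Six from one sequence: 20% × 20/26 = 15.4% fasting; 20% × 12/18 = 13.3% fed. The other product still prints 20%, so the table shows a spurious gap of 4.6 or 6.7 percentage points.

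**The case against.** **No sentence states the adverse event denominator.** The SAP 11 rule is general, and its remark about a separate category for missing observations suggests it was written for categorical variables with missing values. That is fair as to intent. But the rule applies unless something else is stated, and SAP 17.1.1 states nothing else.

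**The set may narrow to the column.** Using 26 and 18 rather than 44 already narrows the analysis set to the food group, and SAP 11 asks for presentation by treatment as well as by food condition. One could narrow again to those who took the treatment. That is the sensible outcome, but the text does not deliver it: food group divides the subjects, whereas in a crossover treatment does not. A programmer could reasonably go either way.

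**The shells may settle it.** SAP 11 says the shells describe the format and content of the tables, and they carry the same final date as the SAP. They were not supplied. If they already set column Ns by exposure, only the SAP text needs aligning. This stands as a limit.

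**The extreme is unlikely.** The floors of 20 and 12 count evaluable subjects, not subjects dosed in Period 2. Someone dosed twice but not evaluable causes no dilution, and someone never dosed is outside the Safety Population. Subjects are inpatients from Day -1 to Day 10, and Protocol 5.6 expects very little premature withdrawal for safety reasons. Protocol 8.5.4 also speaks of the first four, not six, fed discontinuations going unreplaced. All of this stands: a reader might infer that the plan expects errors of a quarter or a third, and the documents do not support that.

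**The right N is recoverable.** SAP 12.1 counts subjects treated in each period by sequence within food group, and SAP 15 lists every administration. This stands too, but a table should not need its reader to recompute it.

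**Conclusion.** The point holds on the supplied text. The default denominator applies to the by-treatment percentages in SAP 17.1.1, and it understates a product's incidence by d/N: 3.8% relative per unexposed subject in the fasting group and 5.6% in the fed group. It is nil if every subject receives both products. The values of 23.1% and 33.3% are the limit for six losses before any replacement, all between doses and all from one sequence. Beyond six, replacements change both d and N. The percentages overall and by food group are sound, since everyone in the Safety Population has had at least one dose.

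Two stronger readings should be resisted. A reader might infer that a formal safety comparison is compromised. The secondary objective is to examine safety and tolerability; comparison is named only for the additional pharmacokinetic parameters, and SAP 17 keeps safety descriptive. A reader might also infer an effect on the bioequivalence conclusion. There is none, because that analysis uses the PK Population and does not use these percentages.

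The conclusion assumes that the shells do not already state a different denominator.

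**What to change.** Add to SAP 17.1.1: *For by-treatment summaries, the denominator is the number of Safety Population subjects in that food group who received that treatment.* Show that N in each column header. Repeat the sentence in SAP 17.1.2 if that table has by-treatment columns, and check that the shells agree. The cost is one sentence and one programmed denominator. No new data are needed, because SAP 12.1 already counts subjects treated in each period by sequence within food group. It should be settled before database lock, so that the denominator is not chosen after the withdrawals are known.

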7.1.3 Period 1 (Day 1 administration to 48 hours post administration)

Day 1, IMP Administration

On Day 1, the following assessments will be conducted and/or collected and recorded on the eCRF.

Trial Eligibility Assessments

Subjects will be assessed for vital signs (blood pressure, pulse rate, temperature and respiration). Blood pressure assessments determine eligibility to be randomized to the trial. The blood pressure (measured in sitting position after at least 5 minutes rest) normal range is considered ≥ 90 mmHg and ≤ 139 mmHg for SBP; ≥ 60 mmHg and ≤ 90 mmHg for DBP.

Any concomitant medications, diseases and treatments should be documented. Concurrent administration of any medication will be prohibited during the trial (Section 6.5.2).

If the subject is determined to be ineligible for any of the above assessments, the subject will not receive randomized treatment.

Any AEs and serious adverse events (SAEs) should also be recorded.

Baseline Sampling

Eligible subjects will have their Baseline blood sample collected at 10 minutes before GIR administration in Period 1 for both the fasting and fed group subjects.

Administration of IMP

As per randomization, each subject will receive a single dose of test GIR (Sequence A-B) or reference GIR (Sequence B-A) accordingly.

The single dose of GIR administration will occur after 07:00 in the morning of the first day of each period. A total volume of 240 mL water will be consumed with the medication. Following the administration of the drug, hands and mouth will be checked in order to

confirm the consumption of the medication. All subjects will refrain from drinking water during the first 2 hour after drug administration and refrain from eating during the first 4 hours. Standard diet for lunch and dinner will be served for both fasting and fed groups. Beverages should be controlled: fluid intake will be controlled for each inpatient period for all subjects. The subjects should drink approximately 2 L of water during the first 24 hours after drug administration.

Fasting condition and Meal Information Recording

The subjects will have their meals at the research unit on Day 1. The fasting condition; time of breakfast uptake and corresponding time to IMP administration; the scheduled time and exact time of lunch and dinner, will be recorded.

Blood Sampling (Postdose)

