All PK concentrations will be reported and analyzed with the same precision as the source data provided by the bioanalytical laboratory or clinical laboratory regardless of how many significant figures or decimal places the data carry. In export datasets, as well as in the Study Data Tabulation Model (SDTM) PP/XD domain, PK parameters will be provided with full precision, and will not be rounded.

Pharmacokinetic parameters and actual elapsed sample collection times will be rounded for reporting purposes in by-subject listings. Actual elapsed sample collection times will be rounded to two decimal places with units of hours. For PK parameters, the standard rounding procedure will be as follows:

- Parameters directly derived from source data (e.g., C_{max}) will be reported and analysed with the same precision as the source data.
- Parameters derived from actual elapsed sample collection times (e.g., t_{max}) will be reported to two decimal places with units of hours.

- Values of AUC will be rounded to 3 significant figures.
- Percentages not derived directly from source data (e.g., AUC_{extra%}) will be reported to 3 significant figures.
- Other parameters (e.g., $t_{1/2}$, λ_Z , CL_f, V_{z/f}) will be reported with 3 significant figures.

Tables and Descriptive Statistics

All data will be summarized by food condition, treatment or treatment sequence, and/or scheduled time point, as appropriate. Repeated and unscheduled measurements included in the listings will not be used for statistical analyses or summaries, unless the repeated measurement was performed due to unreliable values/technical reasons, e.g., clotted samples. Unscheduled measurements will not be included in by-visit table summaries and graphs, but will contribute to the baseline value and best/ worst case value where required.

Metformin concentration in plasma and its PK parameters will be presented in tables and descriptively summarized by food condition, treatment, and/or nominal time point, as appropriate.

Presentation of PK Concentration Data

Pharmacokinetic concentration data will be descriptively summarized using: number of non-missing observations (N), arithmetic mean (Mean), standard deviation (SD), standard error of the mean (SEM), CV%, minimum (Min), median (Median) and maximum (Max).

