All other statistical analyses will be conducted using SAS[®] Version 9.4 or higher.

Definition of baseline:

Unless otherwise specified, baseline for end of study is defined as the last non-missing measurement taken prior to or on the day of the first IMP administration (including unscheduled assessments as applicable).

For vital signs, the assessment performed within 4 hours prior to IMP administration in each treatment period will be considered as baseline for the treatment period. If there is no time point, the last non-missing assessment prior to dosing in each period will be taken as baseline.

In the case where the last non-missing measurement and the dosing date/time coincide, that measurement will be considered baseline, but medications commencing on the first IMP administration date will be considered post-baseline.

Definition of End of Study

Unless otherwise specified, end of study is defined as the last measurement taken prior to or on the day of discharge (D10 or any special day for Premature Withdrawal Visit).

Definition of duration:

Duration will be calculated by the difference of start and stop date + 1 (e.g. survival time (days) = date of death – date of randomization + 1) (if not otherwise specified).

Conversion factors:

The following conversion factors will be used to convert days into months or years:

1 month = 30.4375 days

1 year = 365.25 days.

Common calculations:

For quantitative measurements, change from baseline will be calculated as:

Test Value at Visit X – Baseline Value

Handling of discontinued subjects and missing data:

Unless otherwise specified, data from discontinued subjects will not be replaced. Handling of missing data for PK parameter calculations are discussed under Section 16.3.2.

In all subject data listings, imputed values will be presented. In all listings imputed information will be flagged.

Missing statistics, e.g. when they cannot be calculated, should be presented as “nd”. For example, if $n=1$, the measure of variability (SD) cannot be computed and should be presented as “nd”. If $n=2$, summaries will not be computed and will be presented as “nd”.

For the derivation of new date variables the following rules will apply:

Partial birth dates will be handled this way: day will be imputed as 15 if it is missing, and month imputed as June if missing. If both of day and month are missing, they will be imputed as July 1st. If year is missing then the date will not be imputed.

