17.4 Vital Signs

The following Vital Signs measurements will be reported for this study:

- Systolic Blood Pressure (mmHg)
- Diastolic Blood Pressure (mmHg)
- Pulse Rate (bpm)
- Temperature (°C)
- Respiratory Rate (breaths/min)

Systolic and diastolic blood pressures (mmHg) and pulse rate (beats/min) measurements as well as body temperature (°C) and respiration (breaths/min) will be presented by descriptive statistics overall and by treatment sequence for each group at baseline and end of study visit, and by group, treatment and time point for the values obtained during the treatment periods as raw data and change from baseline in the corresponding treatment period.

Frequency tables based on the classification of values as Low, Normal, High and Missing with respect to the reference ranges will be summarized by treatment sequence at end of study for each group, and by group, treatment and time point for the values obtained during the treatment period.

All marked abnormal for vital signs values will be listed.

All data will be listed by group, treatment sequence, subject, treatment, visit, and time point.

Markedly abnormal quantitative Vital Sign measurements will be identified in accordance with the following predefined markedly abnormal criteria:

| Variable | Unit | Low | High |
|------------------|------|----------------|-----------------|
| SBP | mmHg | < 85 mmHg | > 139 mmHg |
| DBP | mmHg | < 50 mmHg | > 90 mmHg |
| Pulse rate | bpm | < 50 Beats/min | > 100 Beats/min |
| Body temperature | °C | < 36 °C | > 37.3 °C |

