17.5 Other Safety or Tolerability Evaluations

17.5.1 ECG Evaluation

Results from the 12-Led Electrocardiogram (ECG) be presented by descriptive statistics overall and by treatment sequence for each group at baseline and end of study visit.

The following ECG parameters will be reported for this study:

- RR Interval (ms)
- PR Interval (ms)
- QRS Duration (ms)
- QT Interval (ms)
- QTc (Bazett) (ms)
- QTcF (Fridericia) (ms)
- Heart Rate (beats/min)
- Rhythm

Frequency tables for overall evaluation of ECG based on the classification of values as Normal, ANCS (Abnormal, Not Clinically Significant), ACS (Abnormal, Clinically Significant) and Missing will be presented by treatment sequence and overall for each group at the end of study visit.

12-lead ECG parameters and result of ECG will be listed in individual subject listing by group, treatment sequence, subject, visit, treatment and time point. All marked abnormal values of ECG evaluation will be listed by subject, treatment sequence and group.

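### SAP 11 cuts off the end-of-study baseline by calendar day, so as written the 4-hour post-dose Day 1 ECG becomes the ECG baseline

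*SAP*

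**What the plan says.** Under its definition of baseline, SAP 11 gives a default that applies unless something else is specified. For end-of-study comparisons, baseline is the "last non-missing measurement taken prior to or on the day of the first IMP administration".

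Three other statements in SAP 11 bear on it:

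- Vital signs have their own rule: "the assessment performed within 4 hours prior to IMP administration in each treatment period will be considered as baseline for the treatment period". Where such an assessment is lacking, the SAP has a fallback: "the last non-missing assessment prior to dosing in each period will be taken as baseline".
- There is a tie rule: "In the case where the last non-missing measurement and the dosing date/time coincide, that measurement will be considered baseline".
- Unscheduled measurements stay out of by-visit summaries but "will contribute to the baseline value and best/ worst case value where required".

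SAP 17.5.1 summarises the ECG parameters overall and "by treatment sequence for each group at baseline and end of study visit", and gives no ECG-specific baseline. SAP 17.4 summarises vital signs at baseline and end of study, and also by time point within each period with "change from baseline in the corresponding treatment period".

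On timing, protocol 7.1.3 states: "The single dose of GIR administration will occur after 07:00 in the morning". Protocol 7.1.3 and Table 1 footnote h place a 12-lead ECG 4 hours after dosing on Day 1. Protocol 7.1.2 and Table 1 place one at admission on Day -1. Protocol 6.2 also mentions an ECG before dosing on Day 1.

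**The concern.** A baseline should describe the subject before any drug. A rule that admits anything recorded on the dosing day, and then takes the last such value, selects the latest reading of that day. For ECG that is a scheduled post-dose reading.

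The SAP 17.5.1 table would then show on-drug values under a baseline label. The values would follow the test product in Sequence A-B and the reference in Sequence B-A, and the overall column would mix the two. Someone reading QTc from baseline to end of study would be comparing a value 4 hours after the first dose with a Day 10 value taken after the second. SAP 13.3 refers baseline ECG characteristics to Section 17, so this table is the planned summary of pre-treatment ECG. The true pre-dose values would appear only in the listings.

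**Working it through.** The SAP gives no figure to reproduce here. The check applies the rule to the protocol's ECG schedule and compares it with a cut-off at dosing time.

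**Which ECG is selected**

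| ECG | Source | Eligible by calendar day (SAP 11 as written) | Eligible at or before dosing time |
|---|---|---|---|
| Screening, Day -14 to -2 | Protocol Table 1, 7.1.1 | yes | yes |
| Day -1 | Protocol Table 1, 7.1.2 | yes | yes |
| Day 1 pre-dose | Protocol 6.2 only | yes | yes |
| Day 1, 4 h post-dose | Protocol Table 1 footnote h, 7.1.3 | yes | no |
| Day 8, 4 h post-dose | Protocol Table 1 footnote h, 7.1.6 | no | no |
| Day 10 | Protocol Table 1 footnote h, 7.1.6 | no | no |

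With a morning dose, the 4-hour reading falls on the same calendar day. The last eligible record is therefore:

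- as written: the Day 1 4-hour ECG, whether or not the pre-dose ECG of protocol 6.2 was taken;
- with a dosing-time cut-off: the Day 1 pre-dose ECG if taken, otherwise the Day -1 ECG.

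**Is the 4-hour value on drug?** Protocol 5.5.2 equates 4 hours with twice the median tmax, so the implied median tmax is 4 / 2 = 2 h. The reading comes after the expected peak.

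**How many subjects and summaries**

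- Allocation (SAP Table 5): fasting 13 + 13, fed 9 + 9.
- First dose test: 13 + 9 = 22. First dose reference: 13 + 9 = 22. Total 44.
- Baseline columns: 2 food groups x (2 sequences + overall) = 6.
- Quantitative parameters in SAP 17.5.1: RR, PR, QRS, QT, QTc Bazett, QTcF, heart rate = 7.
- Baseline summaries affected: 7 x 6 = 42, plus rhythm.

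These are counts, not effect sizes. The documents give no figure for how far an ECG value moves at 4 hours. A subject without a 4-hour ECG would fall back to a genuine pre-dose value, so with missing data the column would mix both kinds.

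**Other data under the same default**

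- *Laboratory:* the last scheduled sample before Day 10 is on Day -1, so the scheduled baseline is correct. Only an unscheduled post-dose sample on Day 1 could be caught, because unscheduled values may feed the baseline.
- *Vital signs within a period:* protected by their own pre-dose rule.
- *Vital signs, baseline against end of study (SAP 17.4):* arguable. The pre-dose rule is worded for the treatment-period baseline, but its fallback sentence can also be read as governing here.

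**The case against.** The strongest reply is that the whole paragraph points to a dosing-time cut-off. The tie rule would be unnecessary if every same-day measurement already qualified, and it refers to date and time for measurements but only to the date for medications. The words about the day of first administration may have been chosen simply to keep the pre-dose Day 1 readings of protocol 6.2. Protocol Table 1 heads the screening column as baseline, protocol 7.1.1 lists ECG among the baseline assessments, and SAP 13.3 treats the ECG baseline as a baseline characteristic. The table shells, which were not available, may name the baseline visit. A programmer might well take the pre-dose value.

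Much of this stands as evidence of intent. It does not change what the rule says. The tie rule settles a measurement that coincides with dosing and does not exclude a later one. The SAP definition does not adopt the protocol's screening label: it takes the last value up to Day 1. That the shells might correct the text is no reason to leave the text as it is.

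The reply is also right that the stakes are small. No ECG change from baseline or ECG shift table is planned, the ECG frequency table is for end of study only, and all values are listed by visit and time point.

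**Conclusion.** The concern holds. Read as written, SAP 11 makes the 4-hour post-dose Day 1 ECG the baseline for up to 44 subjects and 42 ECG summaries plus rhythm. This is a stated rule that gives the wrong value, not a missing detail.

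Severity is minor. Only descriptive safety columns are affected. The bioequivalence analysis, the treatment-period vital-sign changes and the scheduled laboratory baselines are not.

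The conclusion rests on the SAP wording and the protocol schedule, and on the 4-hour ECG being recorded. Whether the produced table would carry the error also depends on the shells and on how the rule is programmed.

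**What to change.** In SAP 11, replace the calendar-day wording so that baseline is the last non-missing measurement taken at or before the date and time of the first IMP administration. State that this applies to ECG and to the baseline and end-of-study summary of vital signs. This agrees with the existing tie rule and would also exclude an unscheduled post-dose laboratory sample.

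The cost is one sentence. It needs no new output and no new data: a Day -1 ECG is scheduled for every subject, and protocol 7.1.1 and 7.4.4 require the date and time on each ECG printout.

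Separately, protocol 6.2, which has an ECG before dosing on Day 1, should be reconciled with Table 1 footnote h and section 7.1.3, which give only the 4-hour ECG for that day. The revised baseline definition works whichever way that is settled.
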